Appendix 2: Derivations of all outcome measures

Scored Measures

1. Red flag (binary variable)

Red flags will be considered "present" if the patient reports **ALL** of the criteria for pain, vomiting, weight loss, inability to eat, constipation, stool, fever **OR** rectal bleeding listed below.

A red flag from **pain criteria** will be indicated if **ALL** of the following criteria are present:

- 1. The patient has severe stomach pain that may or may not be worse after eating.
- 2. The patient has experienced this pain for less than three weeks.
- 3. The patient has not spoken to a doctor or nurse about this pain.
- 4. The patient has not had any investigations performed by their healthcare team for this pain.
- 5. The patient has not had any cause diagnosed for this pain.

A red flag from **vomiting criteria** will be indicated if **ALL** of the following criteria are listed:

- 1. The patient has regular or persistent vomiting.
- 2. The patient has experienced vomiting for less than two weeks.
- 3. The patient has not spoken to a doctor or nurse about this vomiting.
- 4. The patient has not had any investigations performed by their healthcare team for this vomiting.
- 5. The patient has not had any cause diagnosed for this vomiting.

A red flag from **weight loss criteria** will be indicated if **ALL** of the following criteria are listed:

- 1. The patient has recently experienced unintentional, rapid weight loss without trying to lose weight.
- 2. The patient has experienced this weight loss for less than two weeks.
- 3. The patient has lost more than 5 kilograms (10 pounds).
- 4. The patient has not spoken to a doctor or nurse about this weight loss.
- 5. The patient has not had any investigations performed by their healthcare team for this weight loss.
- 6. The patient has not had any cause diagnosed for this weight loss.

A red flag from **inability to eat** criteria will be indicated if **ALL** of the following criteria are listed:

- 1. The patient is unable to eat anything except a very soft diet because solid food causes pain.
- 2. The patient has experienced this inability to eat for less than two weeks.
- 3. The patient has not spoken to a doctor or nurse about this inability to eat.

PCTU_TEM_ST_02 Statistical Analysis Plan template v3.0 Study IBD-BOOST OPTIMISE Document version 1.0

- 4. The patient has not had any investigations performed by their healthcare team for this inability to eat.
- 5. The patient has not had any cause diagnosed for this weight loss.

A red flag from **constipation** criteria will be indicated if **ALL** of the following criteria are listed:

- 1. The patient has constipation plus inability to pass gas and a very distended abdomen.
- 2. The patient has experienced this constipation for less than two weeks.
- 3. The patient has not spoken to a doctor or nurse about this constipation.
- 4. The patient has not had any investigations performed by their healthcare team for this constipation.
- 5. The patient has not had any cause diagnosed for this constipation.

A red flag from **stool** criteria will be indicated if **ALL** of the following criteria are listed:

- 1. The patient has had new symptoms over the past two weeks that comprise passing dark, black, treacle-like stools.
- 2. The patient has experienced this black stool for less than two weeks.
- 3. The patient has not spoken to a doctor or nurse about these stools.
- 4. The patient has not had any investigations performed by their healthcare team for these black stools.
- 5. The patient has not had any cause diagnosed for these black stools.

A red flag from **fever** criteria will be indicated if **ALL** of the following criteria are listed:

- 1. The patient experiences fevers not due to an obvious reason such as the 'flu' or symptoms of COVID-19.
- 2. The patient has experienced these fevers for less than two weeks.
- 3. The patient has not spoken to a doctor or nurse about these fevers.
- 4. The patient has not had any investigations performed by their healthcare team for these fevers.
- 5. The patient has not had any cause diagnosed for these fevers.

A red flag from **rectal bleeding** criteria will be indicated if **ALL** of the following criteria are listed:

- 1. The patient experiences more than just a few drops of rectal bleeding.
- 2. The patient has experienced this rectal bleeding for less than two weeks.
- 3. The patient has not spoken to a doctor or nurse about this rectal bleeding.
- 4. The patient has not had any investigations performed by their healthcare team for this rectal bleeding.
- 5. The patient has not had any cause diagnosed for this rectal bleeding.

2. PROMIS fatigue score

The fatigue score is based on responses to four questions: items fatigue3-fatigue9 in the RSD. Each question has 5 responses, coded 1 (i.e., "Not at all") to 5 (i.e., "Very much"). The raw score is the sum of the four responses, and ranges from 4 to 20. The score is invalid if any answers are missing. The raw score can then be converted to a T-score based on the table below

PROMIS Adult v1.0 Fatigue 7a				
Short Form Conversion Table				
Raw Score	T-score	SE		
4	33.7	4.9		
5	39.7	3.1		
6	43.1	2.7		
7	46.0	2.6		
8	48.6	2.5		
9	51.0	2.5		
10	53.1	2.4		
11	55.1	2.4		
12	57.0	2.3		
13	58.8	2.3		
14	60.7	2.3		
15	62.7	2.4		
16	64.6	2.4		
17	66.7	2.4		
18	69.0	2.5		
19	71.6	2.7		
20	75.8	3.9		
*SE = Standard Error on T-score metric				

Interpretation note: A higher PROMIS T-score represents more of the concept being measured. For negatively worded concepts like fatigue, a T-score of 60 is one SD worse than average. By comparison, a fatigue T-score of 40 is one SD better than average.

3. PROMIS pain intensity score

The pain intensity score is based on responses to three questions: items pain4, pain5, and pain6 in the Requirements Specification Document (v4.0, 24.08.2021). Each question has five responses, coded 1 (i.e., "Had no pain") to (i.e., "Very severe pain") 5. The raw score is the sum of the 3 responses, and ranges from 3 to 15. The score is invalid if any answers are missing. The raw score can then be converted to a T-score based on the table below.

PROMIS Adult v1.0 Pain Intensity 3a Short Form Conversion Table				
Raw Score	T-score	SE		
3	36.3	5.4		
4	43.1	3.9		
5	47.5	3.7		
6	51.4	3.8		
7	54.8	3.9		

Study IBD-BOOST OPTIMISE Document version 1.0

8	58.5	3.9	
9	61.9	3.8	
10	64.9	3.9	
11	68.4	4.1	
12	72.0	4.2	
13	75.1	4.8	
14	77.8	5.0	
15	81.8	4.2	
*SE = Standard Error on T-score metric			

Interpretation note: A higher PROMIS T-score represents more of the concept being measured. For negatively-worded concepts like Pain Intensity, a T-score of 60 is one SD worse than average. By comparison, a Pain Intensity T-score of 40 is one SD better than average.

4. PROMIS bowel incontinence score

The bowel incontinence score is based on responses to four questions: items urgency3-urgency6 in the RSD. Each question has five responses, coded 1 (i.e., "No days"/ "Never") to 5 (i.e., "6-7 days"/"Always"). The raw score is the sum of the five responses, and ranges from 4 to 20. The score is invalid if any answers are missing. The scores are not based on item response theory models; therefore, there is no T-score. The raw score is then used for statistical analysis. Higher scores indicate increased incontinence. No items can be skipped and there are no screening questions.

5. IBD control score

The IBD-Control-8 sub-score is the sum of RSD items ibdcontrol1, ibdcontrol2, and ibdcontrol4ibdcontrol9. The range of scores is 0-16, with 0 indicating worse control and 16 indicating best control. Responses to each individual item comprise: zero points for the least favourable reply; one point for an intermediate/indeterminate reply, and; two points for the most favourable reply. Note that N/A, denoted 999, is actually counted as 1 for item ibdcontrol2. If ibdcontrol2 has the value 999, treat it as having the value 1 to sum the score. The IBD-Control-VAS score indicates selfreported overall level of control and ranges from 0-10, with 0 indicating worst control.

6. EQ-5D-5L

Each of the five dimensions, mobility, self-care, usual activities, pain/discomfort, and anxiety/depression, comprising the EQ-5D descriptive system is divided into five levels of perceived problems:

LEVEL 1: indicating no problem LEVEL 2: indicating slight problems LEVEL 3: indicating moderate problems LEVEL 4: indicating severe problems LEVEL 5: indicating unable to/extreme problems A unique health state is defined by combining one level from each of the five dimensions. Levels 1-5 are coded as 1-5, respectively, and combining a level for each dimension gives a five-digit health state. These health states are then converted to an indexed value using the EQ-VT for England. The Index value set calculators are found on the Euroqol website and have been saved in the BOOST BCC folder as a Stata do file (Z:\STATISTICIANS\IBD-BOOST\EQ-5D-

Study IBD-BOOST OPTIMISE Document version 1.0

5L index value calculator). The EQ-VAS score is continuous and ranges from 1-100, with 100 indicating "the best health you can imagine" and 0 indicating "the worst health you can imagine." This score shows the patient's perceived overall health and requires no further derivation.

Requirements Specification Document Primary Clinical Outcomes

Clinical outcome – Abnormalities detected on blood test in people with fatigue

- Optimisation CRF: **130. fatiguenew D1.1**. Were new tests ordered for causes of fatigue? If that answer is YES and then **198. ftginterven E1.1.** Were interventions for fatigue advised or prescribed? If that is YES that means there was something abnormal.

Clinical outcome – Irritable Bowel Syndrome or functional dyspepsia indicated in people with pain (by responses on checklist)

- Optimisation CRF: **266. paininterven F1.1.** Were interventions for pain advised or prescribed? If that is a YES that means they had IBS or functional dyspepsia pain. We use a scoring system for these which I can send if helpful using the answers on the checklist. Redcap does this automatically. You can see this on the RSD section 3.7 questions 4 and 5.

Clinical outcome - Untreated loose stool detected in people with faecal urgency.

- Optimisation CRF - **280. urgencyadv G1.1. Were interventions for urgency advised or prescribed?** If this is a YES it means they had untreated urgency.

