- Active disease (defined as faecal calprotectin \geq 200 and/or IBD control score \leq 13).
- Participants for whom interventions for fatigue are advised or prescribed (based on detected blood test abnormalities).
- Participants for whom interventions for pain are advised or prescribed (based on irritable bowel syndrome or functional dyspepsia, as diagnosed from responses on checklist).
- Participants for whom interventions for faecal urgency are advised or prescribed (based on the detection of untreated loose stool).

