6.6 Analysis of the primary clinical outcomes

To fulfil the primary study objective, the proportion of study participants with (i) red flags, (ii) active IBD disease, (iii) blood test abnormalities (in participants with fatigue), (iv) irritable bowel syndrome or functional dyspepsia (in participants with pain), and (v) untreated loose stool (in participants with urgency) will be estimated. We will construct 95%CIs around proportion estimates using Wilson's Score Interval to minimize the loss of coverage that typically occurs with normal approximations of the Wald Interval. Complete case analyses (ignoring missing data) will be performed for primary outcomes.

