Participants advised or prescribed interventions for fatigue	n (%)
Participants advised or prescribed interventions for pain	n (%)
Participants advised or prescribed interventions for faecal urgency	n (%)
Clinical intervention indicated by algorithm	n (%)
Algorithm-informed intervention declined	n (%)
*(faecal calprotectin test \geq 200 and/or IBD control score \leq	:13)

Table 5: PROMIS scores for pain, fatigue, and bowel incontinence at baseline and three months after checklist implementation in participants for whom algorithm-informed interventions were,

and were not, indicated

Outcome	Intervention indicated mean (SD)	No intervention indicated mean (SD)
PROMIS – Fatigue (T-Score)		
Baseline Three months		
PROMIS – Pain Intensity (T-Score)		
Baseline Three months		
PROMIS – Bowel Incontinence (Raw Score) Baseline Three months		
IBD-Control score (Raw Score)		
Baseline Three months		
IBD-Control VAS (Raw Score)		
Baseline Three months		
EQ-5D-5L Baseline Three months		
EQ-5D-5L VAS		
Baseline Three months		

Table 6: Number (n) and percentage (%) of missing data for PROMIS pain intensity, fatigue, and bowel incontinence scores at baseline and three months after checklist implementation in participants for whom algorithm-informed interventions were, and were not, indicated

Outcome	Intervention indicated n (%)	No intervention indicated n (%)
PROMIS – Fatigue (T-Score)		
Baseline		
Three months		
PROMIS – Pain Intensity (T-Score)		
Baseline		
Three months		
PROMIS – Bowel Incontinence (Raw Score)		
Baseline		
Three months		
IBD-Control score (Raw Score)		
Baseline		
Three months		
IBD-Control VAS (Raw Score)		
Baseline		
Three months		
EQ-5D-5L		
Baseline		
Three months		
EQ-5D-5L VAS		
Baseline		
Three months		

Table 7. Adjusted* mean PROMIS (pain, fatigue, and bowel incontinence) and EQ-5D-5L scores at three months after algorithm-informed interventions were indicated

Outcome	Intervention indicated mean (SD)	Missing n (%)
PROMIS – Fatigue (T-Score)*		
PROMIS – Pain Intensity (T-Score)*		
PROMIS – Bowel Incontinence (Raw Score)*		
IBD-Control score (Raw Score)*		
IBD-Control VAS (Raw Score)*		
EQ-5D-5L*		
EQ-5D-5L VAS*		

*adjusted for confounders: baseline measure for each outcome variable, inflammatory bowel disease diagnosis, and NHS

trust

Table 8 Total eligible sample size (N), and the number (n) and percentage (%) of participants completing outcomes on the feasibility of the self-report checklist and management algorithm

Ν	n (%)
	N

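### Primary clinical outcomes (iii)–(v), for fatigue, pain and urgency, have conflicting numerators and denominators across SAP 4.1, 6.6, Appendix 2 and Tables 4 and 10, and Appendix 2 reads advice given as abnormality present

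*SAP*

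**What the plan says.** Four parts of the SAP define these outcomes.

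- **Section 6.6**, which is written to meet the primary objective, estimates "iii) blood test abnormalities (in participants with fatigue"), "iv) irritable bowel syndrome or functional dyspepsia (in participants with pain"), and untreated loose stool among those with urgency. Each is an abnormality, conditional on a symptom.
- **Section 4.1** (and the section 3 summary) takes the proportion of patients, without a symptom condition, and lists "Participants for whom interventions for fatigue are advised or prescribed (based on detected blood test abnormalities"). Pain and urgency follow the same pattern, each with its supposed basis in brackets.
- **Tables 4 and 10** carry the row "Participants advised or prescribed interventions for fatigue" and its pain and urgency counterparts. Table 4 gives percentages of the non-missing. Neither table names a symptom subset.
- **Appendix 2** uses headings that match 6.6 but derives each outcome from the Optimisation CRF. Fatigue needs a YES to new tests ordered and then a YES to interventions: "If that is YES that means there was something abnormal". Pain needs a YES to interventions: "If that is a YES that means they had IBS or functional dyspepsia pain". Urgency needs a YES to interventions: "If this is a YES it means they had untreated urgency". The pain entry adds that REDCap already scores IBS and functional dyspepsia automatically from the checklist.

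**The concern.** Objective 1 in section 3 asks what proportion of symptomatic participants have treatable contributors. The CRF, as section 4 describes it, records what the clinical team planned to do. Having a contributor and being advised an intervention come apart whenever an abnormality is not acted on, or advice is given for another reason. Section 1.3 itself reports equipoise among clinicians about whether these causes need addressing, so the plan cannot assume that the two coincide.

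Two analysts working from this SAP could therefore report different numbers for the same named primary clinical outcome, and either could present a count of advice as a prevalence of abnormality.

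**Working it through.** **1. Numerator.** The hypothetical participants below are classified under each definition. The first three have fatigue and the fourth has pain.

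| Participant | 6.6 | Table 4 row | Appendix 2 |
|---|---|---|---|
| Abnormal existing blood result, intervention advised, no new tests ordered | counted | counted | not counted |
| New tests ordered and abnormal, no intervention recorded | counted | not counted | not counted |
| New tests ordered and normal, intervention advised for another reason | not counted | counted | counted |
| Checklist score positive for IBS or functional dyspepsia, no intervention recorded | counted | not counted | not counted |

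The first row separates Appendix 2 from the table it is meant to feed, because the new-tests condition appears only in Appendix 2. The other rows separate 6.6 from both. In the third row the bracket in 4.1, read strictly, would exclude the participant, but neither the Table 4 row nor the CRF rule applies that bracket.

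For pain, the quantity named in 6.6 is available directly, since the checklist score exists, yet Appendix 2 infers it from the advice item. For urgency, the heading names untreated loose stool and the explanation concludes untreated urgency.

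**2. Denominator.** Section 6.6 restricts to the symptomatic; 4.1 and Tables 4 and 10 do not. The SAP gives no rule for who counts as having fatigue, pain or urgency.

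**3. The plan's own precision figure.** Section 5.1a gives a maximum 95% CI width of 13.9% for N = 200 by normal approximation.

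Width = 2 × 1.96 × √(0.5 × 0.5 / n)

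n = 200: 2 × 1.96 × √(0.25/200) = 13.86%, that is 13.9%. The figure reproduces (Wilson, the method in 6.6: 13.7%).

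**4. What a symptomatic denominator would do.** The numbers with each symptom are not given. As an assumption only, take the background figures in the Introduction (fatigue 41%, pain 62%, continence difficulty up to 75%, all in remission) and apply them to 200.

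| Subset | n assumed | Max width, Wald | Max width, Wilson | 20 positives as % of n | Ratio to % of 200 |
|---|---|---|---|---|---|
| All participants | 200 | 13.9% | 13.7% | 10.0% | 1.00 |
| Urgency | 150 | 16.0% | 15.8% | 13.3% | 1.33 |
| Pain | 124 | 17.6% | 17.3% | 16.1% | 1.61 |
| Fatigue | 82 | 21.6% | 21.2% | 24.4% | 2.44 |

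The count of 20 is arbitrary. The ratio is 200/n whatever the count, for example 200/82 = 2.44. If every participant had the symptom, the ratio would be 1 and the width would stay at 13.9%.

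**The case against.** The best reply is that 6.6 is the outlier. Section 3, section 4.1, Tables 4 and 10 and the CRF items all count interventions advised or prescribed, and the brackets in 4.1 tie the advice to the abnormality. The authors evidently meant the definitions to coincide, and apart from the fatigue condition an analyst following Appendix 2 and Table 4 would reach nearly the same numerator. That much stands. It does not make advice equal to abnormality, settle the denominator, or remove the extra fatigue condition.

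It is also fair that the CRF and the Requirements Specification Document are not shown. If the fatigue, pain and urgency items are completed only for participants with that symptom, Table 4's non-missing percentage could match the 6.6 denominator. The SAP does not settle this, so the absence of a symptom rule is a reason to state one and does not prove that none exists.

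Three stronger readings are tempting and are not supported:

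- A reader might infer a definite bias in the reported proportions. That would need the sensitivity and false-positive rate of the CRF items, and the document gives neither.
- A reader might infer that clinical teams at some sites that act less would appear to have healthier patients. Section 6.10 breaks down only feasibility outcomes by Trust; no site comparison of these outcomes is planned.
- A reader might take 82 as the expected number with fatigue. The 41% refers to people in remission, whereas participants here had asked for symptom support, so the true subset may be larger and the denominator effect smaller.

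Finally, the study is descriptive and its main focus is now feasibility. That limits the consequences, but these remain the named primary clinical outcomes.

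**Conclusion.** The concern holds as an inconsistency of definition. Following the SAP's stated rules gives conflicting numerators and denominators for primary clinical outcomes (iii)–(v), and Appendix 2 equates advice with presence of disease. This rests on the text alone and needs no assumed figures.

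The numerical effect cannot be determined from the document. Under the assumed subset sizes, the choice of denominator alone changes a reported percentage by a factor between 1 (everyone symptomatic) and 2.44 (82 with fatigue), and the maximum CI width lies between 13.9% and about 21.6%. The 13.9% is correct for N = 200; it simply does not carry over to smaller subsets.

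**What to change.** 1. Set one numerator and one denominator for each of the three outcomes, and word them identically in 4.1, 6.6, Appendix 2 and Tables 4 and 10.
2. If the 6.6 denominators are kept, state the rule for being symptomatic, and note in 5.1a that the 13.9% maximum width applies to 200 participants and not to the subsets.
3. For pain, derive IBS or functional dyspepsia from the automatic REDCap checklist score, and report *intervention advised* as a separate row.
4. For fatigue and urgency, derive the contributor from recorded results or checklist items only where these are captured in analysable form. The SAP does not show that they are. Otherwise label the row *intervention advised or prescribed* and do not interpret it as prevalence of abnormality.
5. Reconcile the new-tests condition for fatigue with Table 4: either apply it in both places or remove it.

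The cost is revised SAP text and a few more table rows. The pain score already exists; whether the fatigue and urgency contributors can be derived depends on what the CRF and checklist hold, and item 4 covers the case where they cannot.

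### Section 6.6 promises the proportion with a condition, but the Appendix 2 rules count interventions advised or prescribed and assert that the two are the same

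*SAP*

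**What the plan says.** The SAP describes these primary clinical outcomes in two ways.

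- **As a condition.** Section 6.6 ties the primary objective to prevalence: "iv) irritable bowel syndrome or functional dyspepsia (in participants with pain), and (v) untreated loose stool (in participants with urgency) will be estimated". Blood test abnormalities in participants with fatigue stand just before these in the same list. The three outcome headings at the end of Appendix 2 are also worded as conditions.
- **As an action.** Sections 3 and 4.1 define the pain outcome as "Participants for whom interventions for pain are advised or prescribed (based on irritable bowel syndrome or functional dyspepsia, as diagnosed from responses on checklist" and the urgency outcome as "Participants for whom interventions for faecal urgency are advised or prescribed (based on the detection of untreated loose stool". The fatigue outcome has the same form, based on blood abnormalities. Tables 4 and 10 label their rows by intervention.

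The Appendix 2 rules use clinician CRF items. Pain is F1.1: "Were interventions for pain advised or prescribed? If that is a YES that means they had IBS or functional dyspepsia pain". Urgency is G1.1: "If this is a YES it means they had untreated urgency". Fatigue needs YES on both D1.1 (new tests ordered) and E1.1 (intervention given), which is then read as an abnormality having been found. Under pain, the text adds: "We use a scoring system for these which I can send if helpful using the answers on the checklist. Redcap does this automatically". It points to RSD section 3.7, questions 4 and 5, but does not make that score the derivation.

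**The concern.** Objective 1 asks how many participants have a treatable medical contributor, and 6.6 offers these proportions as the answer. An action item answers another question: what the clinical team chose to do. The two agree only if every participant with the condition is advised an intervention and nobody else is. Otherwise the action count is a biased estimate of prevalence, and the Wilson interval planned in 6.6 will not show that bias.

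An analyst following 6.6 and one following 4.1 could also report different primary results from the same data. For pain, the first could use the checklist score and the second F1.1.

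**Working it through.** **1. The passages side by side**

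| Outcome | Section 6.6 and Appendix 2 heading | Sections 3 and 4.1, Tables 4 and 10 | Appendix 2 rule |
|---|---|---|---|
| Fatigue | Blood test abnormality | Intervention | D1.1 and E1.1 both YES |
| Pain | IBS/functional dyspepsia | Intervention | F1.1 YES |
| Urgency | Untreated loose stool | Intervention | G1.1 YES, read as untreated urgency |

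The rules fit the third column. They are linked to the second only by the statement that YES means the condition was there. For urgency that statement also names something else: urgency and loose stool are not the same.

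**2. Where the SAP itself lets action and condition part**

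- *Red flags.* The flow diagram description in 6.3 has a group with a red flag for whom OPTIMISE intervention stops. Such a participant can score positive for IBS on the checklist and still have F1.1 as NO or blank.
- *CRF return.* Whether the clinical team returns the CRF is a feasibility outcome (section 4), so non-return is expected to some degree. Section 6.6 uses complete cases and Table 4 uses the percentage of non-missing. A participant with a scored checklist but no CRF therefore drops out.
- *Basis of the advice.* Section 4.1 requires the intervention to rest on the diagnosis. F1.1 and G1.1, as quoted, do not record that basis.
- *Denominator.* Section 6.6 restricts each outcome to participants with the symptom. Table 4 does not state this restriction.

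**3. The plan's own precision figure**

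Section 5.1a gives a maximum 95% interval width of 13.9% for n = 200. Check: 2 × 1.96 × √(0.25/200) = 0.1386, or 13.9%. It reproduces, with a half-width of about 6.9 points. The Wilson interval named in 6.6 has width 13.7% at a proportion of 0.5. Neither depends on which definition is used.

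**4. Illustration of the possible error**

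Let π be the true prevalence, s the probability of advice given the condition, and f the probability of advice without it. The reported proportion is π·s + (1 − π)·f. The SAP gives none of these; all values here are assumed. With π = 0.40:

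- s = 0.8, f = 0: 0.40 × 0.8 = 0.32, error −8 points
- s = 0.6, f = 0: 0.40 × 0.6 = 0.24, error −16 points
- s = 1, f = 0.1: 0.40 + 0.60 × 0.1 = 0.46, error +6 points
- s = 0.9, f = 0.1: 0.36 + 0.06 = 0.42, error +2 points

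Over π from 0.2 to 0.5, s from 0.6 to 1 and f from 0 to 0.2, the error runs from −20 points (0.5 × 0.6 = 0.30 against 0.50) to +16 points (0.2 + 0.8 × 0.2 = 0.36 against 0.20). It includes zero where the two kinds of misclassification cancel.

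**The case against.** The strongest reply is that intervention advised is the declared outcome. Sections 3 and 4.1 say so in full, Tables 4 and 10 follow, and F1.1 and G1.1 record it directly. The lead-in to 4.1 also accepts detection by the nurse or clinician using the algorithm, so clinical judgement is a planned source. On this view 6.6 and the Appendix 2 headings are loose wording. The protocol, which was not available for this review, may settle which definition governs. The study is also descriptive, with feasibility as its main focus (sections 4 and 6.5).

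Most of that stands, and it narrows the point. It does not remove it: 6.6 is the analysis section, it ties the condition to the primary objective, and the sentences equating YES with the condition are still unsupported.

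Four stronger readings are tempting and should be resisted:

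- *That the conditions are not measured at all.* For pain, the checklist diagnosis is scored in REDCap; it is simply not used.
- *That REDCap also scores loose stool.* Automatic scoring is stated only under pain.
- *That the results tables present clinician behaviour as prevalence.* Their rows are correctly labelled as interventions. The prevalence label is in 6.6 and Appendix 2 only.
- *That the error is about 20 points and exceeds the interval width.* That is one corner of assumed values. Advice given for another reason is possible but not documented. The 13.9% width is for n = 200, whereas 6.6 uses only symptomatic participants; with an assumed 100 of them the maximum width is 2 × 1.96 × √(0.25/100) = 19.6%.

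**Conclusion.** Wrong as written, and it should be fixed; it is not critical. For fatigue, pain and urgency alike, the SAP names one quantity in 6.6 and the Appendix 2 headings, and another in sections 3 and 4.1, Tables 4 and 10 and the Appendix 2 rules. The sentences that bridge them are assertions that the SAP's own red-flag and CRF-return provisions can falsify. The derivation therefore does not estimate the prevalence that 6.6 promises.

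The size of the error cannot be determined from the document. The range in the working rests wholly on assumed prevalence and advice rates, and shows only that the difference could exceed the 6.9-point half-width, not that it will. No sample-size figure depends on the choice.

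**What to change.** - Keep intervention advised or prescribed (E1.1, F1.1, G1.1) as the rows that match 4.1 and Tables 4 and 10. For fatigue, say whether D1.1 is still required, since the table label does not imply it.
- Delete from Appendix 2 every statement that YES means the condition was present, and the leftover note offering to send the scoring system.
- For 6.6, add a separate pain row derived from the REDCap checklist score (RSD 3.7, questions 4 and 5), with participants with pain as denominator.
- For urgency and fatigue, derive the condition from recorded stool and treatment items and blood results if the data hold them. If not, reword 6.6 so that it names the intervention.
- Reconcile untreated urgency with untreated loose stool.

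The cost is SAP wording, one more table row for pain, and a check of the RSD for the urgency and fatigue items. The pain score is already computed, so no new data collection is needed for it.
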